### **2.5.4 Sensitivity analysis**

### **2.5.5 Supplementary analysis**

Two supplementary analysis will be conducted:

- An analysis will be conducted based on the definition for the primary estimand; however, all data from treatment up to Day 29 will be considered
- An analysis will be conducted based on data from Day 3 to Day 29 but by handling the discontinuation from study or lost to follow up on or before Day 29 as specified below:
  - A patient will be considered as responder if invasive mechanical ventilation is not required any time on or after Day 3 and the last clinical status returning to 0 or 1 before early discontinuation from study or lost to follow up
  - A patient with the last clinical status >1 before early discontinuation from study or lost to follow up will be considered as non-responder

The supplementary analyses will apply the same logistic regression model as for the primary estimand.

### **2.5.6 Supportive analysis**

The subgroup analyses (subgroups defined in [Section 2.2.1](#)) will be explored for the primary estimand and by fitting the data from each subgroup to the same logistic regression model as described for the primary analysis. In case of analyses on subgroups with extremely imbalanced sample sizes, the subgroup levels can be combined, if appropriate, while fitting the analysis model. The point estimate and 95% CI for odds ratio for each subgroup will be presented using forest plots.

## 2.6 Analysis of the key secondary objective

The key secondary efficacy analysis is based on FAS. The inferential testing on the key secondary endpoint specified in this section will be performed if the null hypothesis of the primary endpoint is rejected with a two-sided testing with p-value less than 0.05. This testing procedure controls the overall two-sided type-I error rate to less than 0.05 within the study.

### 2.6.1 Key secondary estimand

The key secondary clinical question of interest in this study is: Does the administration of canakinumab reduce 4-week mortality among patients with COVID-19-induced pneumonia and CRS, regardless of other subsequent clinical interventions?

The justification for this secondary estimand is that mortality currently represents the main epidemiological and clinical concern for COVID-19 patients and accumulating evidences suggest coexistence of CRS with severe COVID-19-induced pneumonia. Subsequent clinical interventions, including intensive care when a patient become terminally ill, reflect actual clinical practices, whose needs, scope and effectiveness could potentially be related to the earlier decision of canakinumab administration.

The key secondary estimand includes the following components:

Population: Hospitalized patients with COVID-19-induced pneumonia and CRS.

Endpoint: All COVID-19-related deaths (i.e., all deaths caused by study indication) during the 4-week period after study treatment

Treatment of interest: The randomized study treatment (canakinumab or placebo) added onto SOC with or without additional subsequent clinical interventions.

Handling of remaining intercurrent events:

The treatment policy strategy will be adopted for this key secondary analysis.

- Effect of other subsequent clinical interventions will not be adjusted
- Early study discontinuation or lost to follow-up before Day 29: a patient will be considered as survivor if the last clinical status of 0 or 1; otherwise, the patient will not be included in this key secondary analysis (note: this include deaths which are not marked as caused by study indication).

Summary measure: Odds-ratio comparing 4-week CFR in the canakinumab and control groups.

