## 2.2 Secondary estimands

The key secondary clinical question of interest in this study is: Does the administration of canakinumab reduce 4-week mortality among patients with COVID-19-induced pneumonia and CRS, regardless of other subsequent clinical interventions?

The justification for this secondary estimand is that mortality currently represents the main epidemiological and clinical concern for COVID-19 patients and accumulating evidences suggest coexistence of CRS with severe COVID-19-induced pneumonia. Subsequent clinical interventions, including intensive cares when a patient become terminally ill, reflect actual clinical practices, whose needs, scope and effectiveness could potentially be related to the earlier decision of canakinumab administration.

The key secondary estimand includes the following components:

**Population:** Patients with COVID-19-induced pneumonia and CRS.

**Endpoint:** COVID-19-related death during the 4-week period after study treatment

[figure not shown]
**Treatment of interest:** The randomized study treatment (canakinumab or placebo) added onto SOC with or without additional subsequent clinical interventions.

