**Handling of remaining intercurrent events:**

The treatment policy strategy will be adopted for this key secondary analysis.

- Effect of other subsequent clinical interventions will not be adjusted
- Early study discontinuation or lost to follow-up before Day 29: A patient will be considered as survivor if discharged from hospital with clinical status of 0 or 1

Otherwise, the patient will not be included in this key secondary analysis.

**Summary measure:** Difference and Odds-ratio comparing 4-week CFR in the canakinumab and control groups.

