## **12.5 Analysis of secondary endpoints/estimands**

### **12.5.1 Key secondary endpoint**

The key secondary endpoint is the COVID-19 related death during the 4-week period after study treatment. Hypothesis test for the key secondary analysis will be performed if and only if the null hypothesis for the primary analysis is rejected.

The null hypothesis for the key secondary analysis is that there is no difference in the COVID-19 related death rate (i.e. CFR) in patients treated with canakinumab compared to patients on placebo. The test of the hypothesis will be based on a logistic regression model adjusted for treatment, region and the baseline clinical status. The null hypothesis will be rejected if the observed p-value for treatment comparison (based on the CFR ratio) is less than the significance level of 0.05. Model-based estimates of the CFR and their 95% confidence intervals (CIs), estimate of the CFR ratio and 95% CI, and p-value for comparing canakinumab vs. placebo will be provided.

The number and percent of patients with COVID-19 related death during the 4-week period will also be provided by treatment arms.

The key secondary efficacy analysis is based on FAS. Patients who are lost to follow-up or discontinue early from study before Day 29 will be deemed as survivor if the latest clinical status is 0 or 1 on the 9-point ordinal scale. Otherwise, the patient will not be included in the analysis.

A sensitivity analysis will be provided by considering all patients who lost to follow-up or discontinue early from study before Day 29 as survivors.

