**Table 12-2 Power for key secondary analysis (sample size = 450)**

CFR (%)		Clinically meaningful benefits			Power (2-side $\alpha=0.05$ )
Control	ACZ885	difference	OR	RR	
25	12.5	-12.5	0.43	0.5	92%
20	10	-10	0.44	0.5	83%
15	7.5	-7.5	0.46	0.5	70%

Cases of lost to follow up before patient's recovery (clinical status = 0 or 1 on the 9-point ordinal scale) and before Day 29 is expected to be minimal. Sample size adjustment for key secondary analysis is not planned.

There is no formal hypothesis test or power consideration for other secondary analysis.

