#### **2.5.1 Primary estimand**

The primary clinical question of interest is: Does canakinumab + SoC increase the chance of survival without ever requiring invasive mechanical ventilation among patients with COVID-19-induced pneumonia and CRS after start of treatment, regardless of other subsequent clinical interventions?

The justification for this primary estimand is that it captures the clinical outcome of most interest after the canakinumab administration, which reflects also any effects of additional subsequent interventions potentially due to such clinical decision. In the ongoing COVID-19 pandemic with evolving treatment guidelines and healthcare system burdens, this primary estimand is deemed better to reflect actual clinical practices. In addition, the IV delivery of canakinumab is expected to result in a fast decrease in pharmacologically active IL-1 $\beta$  and to reduce IL-1 $\beta$  signaling to marginal levels within hours. However, clinical signs or symptoms within the 24 hours after treatment may not necessarily reflect such pharmacological effect yet. Therefore, only clinical status starting from Day 3 will be considered for the primary endpoint.

The primary estimand includes the following components:

Population: Patients with COVID-19-induced pneumonia and CRS.

**Endpoint:** Clinical response, defined as survival without ever requiring invasive mechanical ventilation (i.e., 9-point ordinal score $\geq 6$ ) from Day 3 (inclusive) up to day 29 (inclusive). A patient will be defined as a non-responder if the worst clinical status at any time from Day 3 (inclusive) up to Day 29 (inclusive) is requiring invasive mechanical ventilation or death (category 6, 7 or 8 on the WHO 9-point clinical status ordinary scale (Section 5.1)).

**Treatment of interest:** The randomized study treatment (canakinumab or placebo) added onto SoC with or without additional subsequent clinical interventions.

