### **2.5.3 Handling of missing values/censoring/discontinuations**

Missing data due to intercurrent events has been addressed via the handling of intercurrent event under the primary estimand definition.

The primary endpoint is based on clinical status starting from Day 3 (inclusive) post treatment. Patients who died or discontinued from study before Day 3 are excluded from the primary analysis. This is not expected to introduce a bias in favor of either treatment arm since the clinical status is not likely to be affected within two days by the study treatment administered on Day 1.

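### The key secondary asks about 4-week mortality but tests only deaths attributed to COVID-19; a clean all-cause Day 29 death comparison on the FAS should be prespecified beside it, and none is visible

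*SAP*

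**What the plan says.** Protocol 2.2 puts the key secondary question as "Does the administration of canakinumab reduce 4-week mortality among patients with COVID-19-induced pneumonia and CRS", whatever other interventions follow. It justifies the estimand by mortality being the main concern. SAP 2.6.1 repeats both under a treatment policy strategy, and SAP 2.6 adds that "The key secondary efficacy analysis is based on FAS".

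The endpoint in both documents is COVID-19-related death over four weeks, which SAP 2.6.1 explains as deaths caused by the study indication. The objective, null hypothesis, conclusion rule and power table are all framed on that endpoint.

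For patients who leave before Day 29 without a qualifying recovered status, Protocol 2.2 says "Otherwise, the patient will not be included in this key secondary analysis". SAP 2.6.1 has the same rule and adds a note on deaths: "the patient will not be included in this key secondary analysis (note: this include deaths which are not marked as caused by study indication"). A patient known to have died of another cause therefore leaves both the numerator and the denominator.

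The nearby analyses that can be seen are:
- **SAP 2.6.4:** marginal standardisation of the same endpoint.
- **SAP 2.6.5:** everyone who discontinued or was lost counts as a non-survivor.
- **Protocol 12.5.1:** "A sensitivity analysis will be provided by considering all patients who lost to follow-up or discontinue early from study before Day 29 as survivors".
- **SAP 2.5.1:** the primary composite, where non-response "is requiring invasive mechanical ventilation or death (category 6, 7 or 8 on the WHO 9-point clinical status ordinary scale"), counted from Day 3. SAP 2.5.3 adds that "Patients who died or discontinued from study before Day 3 are excluded from the primary analysis".
- **SAP 2.5.5:** a version of that composite using all data from treatment onward.
- **SAP 2.8:** descriptive fatal-AE tables and a death listing on the Safety Set.

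**The concern.** This is the trial's only alpha-controlled mortality-type test, and SAP 2.6.2 draws a superiority conclusion from it. Removing known deaths according to attributed cause, a judgement made after randomisation, sits awkwardly with a treatment-policy question about mortality on the FAS. A significant result could be read as a reduction in 4-week mortality when it shows a reduction in deaths attributed to COVID-19.

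The two can part in either direction. Protocol 4.5 reports more fatal infections or sepsis with canakinumab in the earlier cardiovascular trial, at low incidence, yet numerically lower all-cause mortality there. Blinding of sites limits biased attribution but would not hide a real shift in cause of death. Readers need the all-cause result alongside to see whether the two agree.

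**Working it through.** **1. The plan's power figure.** Inputs from Protocol Table 12-2 (SAP Table 3-2): 225 per arm, two-sided 0.05, relative risk 0.5. Power = Φ(|ln OR|/SE − 1.96), with SE = √[1/(225·p₀(1−p₀)) + 1/(225·p₁(1−p₁))].

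- 25% v 12.5%: 0.847/0.254, giving 91.6% (stated 92%).
- 20% v 10%: 0.811/0.278, giving 83.1% (stated 83%).
- 15% v 7.5%: 0.778/0.315, giving 69.6% (stated 70%).

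The table is right for the endpoint it describes.

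**2. Planned against all-cause, 15% v 7.5% row.** COVID deaths are 225 × 0.15 ≈ 34 on placebo and 225 × 0.075 ≈ 17 on canakinumab. The other-cause counts are my assumption, because the documents give no rate. Planned analysis: COVID deaths, with other-cause deaths taken out of the denominators. All-cause analysis: all known deaths over 225. Both use an unadjusted Wald test on the log OR; the plan's model adds region and baseline status.

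Worked case, other-cause deaths 1 v 5 (placebo v canakinumab throughout):
- Planned: 17/220 on canakinumab v 34/224 on placebo. OR = (17/203)/(34/190) = 0.468, SE = √(1/17+1/203+1/34+1/190) = 0.314, p = 0.016, 95% CI 0.25 to 0.87.
- All-cause: 22/225 v 35/225. OR = (22/203)/(35/190) = 0.588, SE = 0.290, p = 0.068, 95% CI 0.33 to 1.04.

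| Other-cause deaths | Planned OR, p | All-cause OR, p |
|---|---|---|
| 4 v 2 (equal share of deaths) | 0.45, 0.012 | 0.45, 0.008 |
| 3 v 3 | 0.46, 0.013 | 0.50, 0.017 |
| 1 v 4 | 0.47, 0.015 | 0.56, 0.048 |
| 1 v 5 | 0.47, 0.016 | 0.59, 0.068 |
| 5 v 1 | 0.45, 0.011 | 0.41, 0.004 |

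Only 1 v 5 loses significance, and the estimate still favours canakinumab. With 57 deaths in all, 22 of them on canakinumab, the hypergeometric chance that at least 5 of 6 other-cause deaths fall on canakinumab is 2.7% if attribution is unrelated to arm.

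**3. The same 1 v 5 split in the other rows.**
- 20% v 10%: 45 v 22 or 23 COVID deaths (225 × 0.10 = 22.5). All-cause 27 or 28/225 v 46/225: OR 0.53 to 0.55, p = 0.016 to 0.023.
- 25% v 12.5%: 56 v 28 COVID deaths. All-cause 33/225 v 57/225: OR 0.51, p = 0.005.

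**4. Does SAP 2.6.5 fill the gap?** SAP 2.6.1 files other-cause deaths under early discontinuation, so I read 2.6.5 as returning them as non-survivors. It also counts living drop-outs as dead. In the 15% row with 1 v 5, the assumed living drop-outs give:
- none: OR 0.59, p = 0.068, the all-cause result exactly;
- 2 v 2: OR 0.61, p = 0.075;
- 6 v 2: OR 0.54, p = 0.024;
- 2 v 6: OR 0.72, p = 0.23.

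The all-cause result stays at 0.59, p = 0.068 throughout if those drop-outs are counted as survivors. So 2.6.5 is close when living drop-outs are few and moves with them when they are not.

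**5. The other visible analyses.** SAP 2.6.4 keeps the cause restriction. The primary and its SAP 2.5.5 version mix any-cause death with ventilation. The Protocol 12.5.1 bound runs the other way: if death counts as discontinuation, it could turn other-cause deaths into survivors. The safety tables make no between-arm comparison on the FAS.

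**The case against.** The strongest reply is that nothing is hidden. The endpoint is labelled COVID-19-related death in the objective, endpoint, null hypothesis, conclusion rule and power section; only the question and its rationale speak of mortality. This stands, and it makes the point one of interpretation and reporting.

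Second, SAP 2.6.5 nearly does the job. Protocol 12.7.2 says loss before "recovery (clinical status = 0 or 1 on the 9-point ordinal scale) and before Day 29 is expected to be minimal", and discharged patients are followed by phone. This largely stands. However, that statement covers only loss before recovery, whereas 2.6.5 counts every drop-out as dead, including recovered patients. The 6 v 2 and 2 v 6 drop-out cases are assumptions without support in the documents.

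Third, fatal AEs are tabulated by arm and deaths are listed, so an all-cause count could be recovered. True, but descriptively, on the Safety Set, and without the planned model.

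Three stronger readings may tempt a reader, and the documents do not support them:
- **That the plan has no all-cause death analysis.** SAP 2.9, the end of SAP Table 1-1 and two bullets of SAP section 4 are redacted and may hold one.
- **That the test is invalid or biased towards canakinumab.** It is valid for its cause-specific null, attribution is made while sites are blinded, and all-cause evidence could be stronger as easily as weaker.
- **That the SAP made an undeclared change.** Protocol 12.5.1 already leaves out early discontinuers whose latest status is not 0 or 1. If death ends participation, the SAP note only clarifies that rule.

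**Conclusion.** The point holds as a mismatch between question and test. The question is 4-week mortality; the test addresses COVID-attributed death after removing known deaths from other causes, and alone it does not answer the question. Confidence is high on the mismatch and moderate on whether a companion analysis is missing, given the redactions.

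The size cannot be settled from the documents. With equal shares of other-cause deaths there is no distortion. In the cases examined, the conclusion changed only with an assumed 1 v 5 split in the lowest-power row of Table 12-2, and not in the other two rows. If other-cause deaths are close to zero, the two analyses coincide, and showing that would itself be useful.

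**What to change.** Before the Day 29 lock, prespecify death from any cause through Day 29 on the FAS, with every known death as an event and the same logistic model. For truly unknown vital status only, show both bounds: all survivors and all non-survivors. Report this beside the COVID-attributed CFR. If a redacted section already contains it, refer to it from SAP 2.6. Describe a CFR result as cause-specific unless the all-cause result agrees.

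Keep the tested endpoint as it is. Replacing it would cost power: by the formula in step 1, with 1, 2 or 3 percentage points of other-cause death added to both arms (assumed), power at 15% v 7.5% would fall from about 70% to 67%, 64% or 62%. Reporting alongside costs no power and no alpha, only one more output from data already collected. Stating in SAP section 4 that deaths from other causes are excluded from the key secondary would be a minor clarification.

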### 2.6.2 Statistical hypothesis, model, and method of analysis

The null hypothesis for the key secondary analysis is that there is no difference in the COVID-19 related death rate (i.e. CFR) in patients treated with canakinumab compared to patients on placebo. The alternative hypothesis is that there is a difference between the two treatment groups.

The superiority of canakinumab over placebo will be concluded if the odds ratio  $<1$  for the COVID-19 related death between canakinumab and placebo and the null hypothesis can be rejected at the two-sided significance level of 0.05.

The test of the hypothesis will be based on a logistic regression model with study treatment, region (North America vs. Europe), baseline clinical status based on the 9-point ordinal scale ( $\leq 4, \geq 5$ ) as factors. Model-based estimates of the CFR and their 95% confidence intervals (CIs), estimate of the odds ratio and 95% CI, and p-value for comparing canakinumab vs. placebo will be provided. In case of model converge problem caused by separability, Firth's penalized maximum likelihood estimation will be performed based on the same logistic regression model. The estimated odds ratio, p-values and 95% CI (all computed by penalized profile likelihood) will be presented.

The number and percent of patients with COVID-19 related death during the 4-week period will also be summarized by treatment arms. The difference in observed response rates between canakinumab and placebo arms will also be presented along with the asymptotic 95% confidence interval.

### **2.6.3 Handling of missing values/censoring/discontinuations**

Missing data due to intercurrent events has been address via the handling of intercurrent event under the key secondary endpoint estimand definition.

### **2.6.4 Sensitivity analysis**

As a sensitivity analysis, the between group difference will also be assessed by rate difference using the marginal standardization method, for which the rate difference will be derived from the predicted rate for every patient as if they had received the study treatment or the placebo using a logistic regression model. The model will be adjusted by treatment, region (North America vs. Europe), and baseline clinical status based on the 9-point ordinal scale ( $\leq 4, \geq 5$ ) as factors. The rate within each treatment arm along with the 95% CI, rate difference along with the 95% CI and p-value will be presented.

### **2.6.5 Supplementary analysis**

A supplementary analysis will be implemented, for which all patients who discontinued from study or lost to follow up will be considered non-survivors in the analysis.

The supplementary analysis will apply the same logistic regression model as for the key secondary analysis.

## **2.7 Analysis of secondary efficacy objective(s)**

### **2.7.1 Secondary endpoints**

The secondary efficacy endpoints include the clinical serologic measurements on markers of inflammation related to CRS in COVID-19 patients with pneumonia:

- ratio to baseline overtime up to Day 29 in CRP
- ratio to baseline overtime up to Day 29 in Serum ferritin
- ratio to baseline overtime up to Day 29 in D-dimer

The ratio to baseline and post baseline value will be summarized by mean, SD, median, Q1, Q3, and geometric statistics (geometric mean, geometric CV, 95% CI of the geometric mean) by treatment arm and visit. The summary is based on data with last observation carry forward

(LOCF) as well as observed data. Only post-baseline observations can be used for LOCF, i.e., for patients without post-baseline observation, baseline should not be used to impute missing data at post-baseline time points.

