Other assessments	
[REDACTED]
 
Standard safety and laboratory assessment will be performed during hospital stay and outpatient visits after discharge from hospital (See Assessment Table).
 
In addition, CRS / [REDACTED]
 

• CRP

• Ferritin

 
[REDACTED]
 
[REDACTED]
 
[REDACTED]
 
Additional Laboratory measurements:
 

• Absolute neutrophil count

• Monocytes

• Lymphocytes

• Lactate dehydrogenase

• D-dimer levels

Data analysis	
An absolute increase of 15% survival without ever requiring invasive mechanical ventilation is considered a clinically meaningful benefit. A total sample size of 450 with 1:1 randomization ratio is planned for the study, which is expected to ensure at least 89% power for the primary analysis. Conditional on the rejection of null hypothesis in primary analysis, and if the true 4-week case fatality rate for the control arm is no less than 15%, there will be at least 70% power to prove if canakinumab leads to a 50% relative reduction in the risk of death.
 
The primary analysis will be performed after all patients complete Day 29 assessment or discontinue early from the study before Day 29. Final analysis will happen after all patients complete the study. The primary analysis follows a treatment policy strategy to estimate the difference and odds ratio between the response rates of canakinumab and control arms. Hypothesis testing will be performed based on the odds ratio estimated using a logistic regression model with study treatment, region and baseline

	
clinical status as covariates. The two-sided type I error will be controlled at 0.05.
 
Key secondary endpoint of 4-week case fatality rate (CFR) will be compared between the two treatment arms using a logistic regression model with study treatment, region and baseline clinical status as covariates. Using a hierarchical testing procedure for familywise 2-sided type I error control at 0.05, the hypothesis test in key secondary analysis will be performed if and only if the null hypothesis in the primary analysis is rejected.
 
Other secondary analyses will include descriptive summaries without hypothesis testing.
 
[REDACTED]
 
Safety summaries will be produced for regular DMC safety monitoring.

Key words	COVID-19 pneumonia, SARS-CoV-2, canakinumab

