## 2 Objectives and endpoints

**Table 2-1 Objectives and related endpoints**

Objective(s)	Endpoint(s)
Primary Objective To demonstrate the benefit of canakinumab + standard of care (SOC) in increasing chance of survival without ever requiring invasive mechanical ventilation among patients with COVID-19-induced pneumonia and CRS	Endpoint for primary objective: Clinical response, defined as survival without ever requiring invasive mechanical ventilation from Day 3 (inclusive) up to Day 29 (inclusive).
Secondary Objective(s) To demonstrate the benefit of canakinumab in reducing 4-week case fatality rate (CFR) among patients with COVID-19-induced pneumonia and CRS regardless of other subsequent clinical interventions	Endpoint(s) for secondary objective(s): COVID-19-related death during the 4-week period after study treatment
To evaluate change in clinical serologic measurements related to CRS in COVID-19 patients with pneumonia	

• Adjusted geometric mean ratio to baseline overtime up to Day 29 in the following clinical chemistry measurements:

• CRP

• Serum ferritin

• D-dimer

To evaluate safety of canakinumab in patients with COVID-19-induced pneumonia and CRS	Number of participants with Adverse Event (AE), serious adverse events (SAE), clinically significant changes in laboratory measures, and vital signs

Objective(s)	Endpoint(s)

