### **12.5.2 Other Secondary objectives and endpoints**

Descriptive statistics (mean, standard deviation, median, minimum and maximum) will be provided for variables that are of the numeric or continuous type, while frequency distributions (with number and percent) will be provided for variables that of the categorical type.

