#### **12.5.4 Biomarkers**

Adjusted geometric mean ratio to baseline in serum ferritin, CRP and D-dimer will be reported by treatment arm and visit.

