### **2.7.2 Statistical hypothesis, model, and method of analysis**

No hypotheses will be tested for the secondary efficacy endpoints listed above and no p-values for the treatment comparisons will be provided.

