### **2.7.3 Handling of missing values/censoring/discontinuations**

The summary is based on data with LOCF for missing data imputation.

For patients who are discharged from hospital before Day 29, biomarker data are not likely to be available after discharge.

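### SAP 2.7 plans only unadjusted summaries by arm for a CRP, ferritin and D-dimer endpoint that the protocol and SAP Table 1-1 define as adjusted (minor)

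*SAP*

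**What the plan says.** Three places define the endpoint as adjusted. Protocol Table 2-1 reads "Adjusted geometric mean ratio to baseline overtime up to Day 29 in the following clinical chemistry measurements", and SAP Table 1-1 repeats that definition. Protocol 12.5.4 gives the reporting rule: "Adjusted geometric mean ratio to baseline in serum ferritin, CRP and D-dimer will be reported by treatment arm and visit".

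SAP 2.7.1 lists the same three markers simply as ratios to baseline. Its plan is: "The ratio to baseline and post baseline value will be summarized by mean, SD, median, Q1, Q3, and geometric statistics". The geometric statistics are the geometric mean, its 95% CI and the geometric CV, by arm and visit. SAP 2.7.2 has a heading that promises a model, but it says only that nothing is tested and "no p-values for the treatment comparisons will be provided".

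On missing data, SAP 2.7.1 runs the summary both with LOCF and on observed values, and bars carrying the baseline value forward. SAP 2.7.3 mentions one version only: "The summary is based on data with LOCF for missing data imputation". It adds that marker data after discharge are unlikely.

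**The concern.** A programmer who follows SAP 2.7 would produce unadjusted geometric means, while the SAP's own objectives table promises adjusted ones. The SAP therefore disagrees with itself as well as with protocol 12.5.4. The visible part of SAP section 4 (changes to protocol-specified analyses) does not mention it.

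The stake is interpretability and precision. Readers will compare the two arms' geometric means. The change in a marker usually depends on its starting value, so unadjusted means move with chance baseline differences.

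A secondary matter concerns late visits. Under protocol Table 8-1, footnote 2, phone visits after discharge take no laboratory tests. A late LOCF value is therefore mostly the discharge value or the last in-hospital value, and no stop at death is stated. If the time of leaving differs by arm, the late LOCF summaries can partly reflect that timing.

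**Working it through.** **Text comparison**

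| Place | Adjusted? | Model or covariates visible? |
|---|---|---|
| Protocol Table 2-1 | Yes | No |
| Protocol 12.5.4 | Yes | No |
| SAP Table 1-1 | Yes | No |
| SAP 2.7.1 | No | No |
| SAP 2.7.2 (no redaction mark) | Silent | No |
| SAP contents, 5.3 Statistical models | n/a | Primary and key secondary only |

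The documents give no power, variability or effect size for these markers, so there is no figure of theirs to reproduce. What follows is illustration only. The one input from the documents is 450 patients at 1:1, which is 225 per arm.

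**Effect of leaving out the adjustment**

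Assumed: SD of log baseline 0.8, 1.0 or 1.2; log ratio falls by 0.3, 0.5 or 0.8 per log unit of baseline; residual SD 0.8.

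- SE of the arm difference in log baseline = SD × √(2/225) = SD × 0.0943, giving 0.075, 0.094 and 0.113.
- Shift in the unadjusted between-arm ratio at a 1-SE imbalance = exp(slope × SE). Lowest case: exp(0.3 × 0.0754) = 1.023. Middle: exp(0.5 × 0.0943) = 1.048. Highest: exp(0.8 × 0.1131) = 1.095.
- At 2 SE the lowest and highest cases are 1.046 and 1.198.
- The plan reports by arm. With equal arms, each arm's own geometric mean moves by half of this on the log scale: exp(0.0226/2) = 1.011 to exp(0.0905/2) = 1.046 at 1 SE.
- CI width, adjusted over unadjusted = √[0.64 / (0.64 + slope² × SD²)]: √(0.64/0.6976) = 0.96, √(0.64/0.89) = 0.85, √(0.64/1.5616) = 0.64. This is a narrowing of 4%, 15% and 36%.

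In 4,000 simulated trials with no true effect, those with an imbalance of at least 1 SE gave average unadjusted ratios of 1.033, 1.075 and 1.149 in the three cases. The adjusted ratios were 0.998, 1.001 and 1.000.

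A second set of assumptions agrees: log SD 1.0 at both times and baseline-to-follow-up correlation 0.2 to 0.6. A 1-SE imbalance multiplies the unadjusted ratio by 0.93 to 0.96, and adjustment cuts the variance to (1 + correlation)/2 = 0.6 to 0.8 of its unadjusted value.

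**LOCF: mechanism only**

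The result depends wholly on what is assumed:

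- Same marker decline in both arms (0.10 log units per day, no plateau), median discharge Day 7 vs 9, log SD 0.4. The gap in mean discharge day is 2 × exp(0.08) = 2.17 days, so the Day 29 ratio is exp(0.10 × 2.17) = 1.24. The arm discharged sooner looks worse. With equal timing the ratio is 1.00.
- A real difference in decline (half-life 3 vs 4 days), with discharge once the marker reaches 10% to 30% of baseline. The Day 7 ratio is about 0.70, but Day 29 LOCF shows about 0.97, so the effect is nearly hidden.
- Equal discharge timing, deaths 7.5% vs 15% (last row of protocol Table 12-2), values carried past death: 0.74 to 0.95, part of which is a real difference between arms.

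**The case against.** The strongest reply is that the protocol itself treats these endpoints as descriptive. Protocol 12.5.2 says "Descriptive statistics (mean, standard deviation, median, minimum and maximum) will be provided for variables that are of the numeric or continuous type", and the protocol summary says "Other secondary analyses will include descriptive summaries without hypothesis testing". SAP 2.7.1 does give geometric mean ratios to baseline with confidence intervals. What is missing is an adjustment that no visible text defines, and no visible text plans a between-arm ratio, which is the quantity illustrated above. Much of this stands, and it is why the point is minor. It does not remove the mismatch. Descriptive means untested, and an adjusted mean with a confidence interval needs no test. Protocol 12.5.4 is the specific text for these markers. Dividing by baseline cannot be the adjustment meant, because the phrase already says ratio to baseline.

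A reader might infer that no adjusted analysis was ever planned, or that the protocol never says what the adjustment is for. The documents do not support that. Protocol 12.4.2, part of the protocol summary, SAP 2.9, SAP 5.3.1 and parts of SAP section 4 are redacted, and any of them could hold a model or a definition.

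On LOCF, three provisions soften the point. Day 29 assessments move to the day of discharge, so the carried value is normally fresh. SAP 2.1.1.6 allows a deliberate summary at discharge or Day 29. Observed-data summaries stand beside the LOCF ones, although at late visits these come mainly from patients still in hospital.

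**Conclusion.** The mismatch holds on the visible text: the endpoint is defined as adjusted in three places, and SAP 2.7 as written produces only unadjusted summaries by arm. Severity is minor. Nothing is tested or powered on this endpoint, so no type I error, sample size or trial conclusion is affected.

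The sizes (2.3% to 9.5% at a 1-SE imbalance, CI 4% to 36% narrower) rest on assumed marker variability and slopes. They apply to a between-arm comparison that readers will make but that the visible SAP does not formally plan.

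A reader might also infer that LOCF biases the late-visit comparison by a known amount or in a known direction. That does not follow. The documents give no marker course, length of stay or discharge gap, and the examples above point different ways. What can be said is that late LOCF values can reflect exit timing if that differs by arm, and that SAP 2.7.1 and 2.7.3 do not agree on which data versions are produced.

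**What to change.** In SAP 2.7.2, specify for each marker a linear model for log ratio to baseline at each visit, on observed values, with treatment, log baseline, region (North America vs. Europe) and baseline clinical status (≤4, ≥5). SAP 2.6.2 already uses the last two covariates. Report adjusted geometric mean ratios by arm and, optionally, the between-arm ratio, with 95% CI and no p-values.

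- If a redacted section already holds such a model, a cross-reference from SAP 2.7 is enough.
- If no adjustment is intended, remove the word *Adjusted* from SAP Table 1-1 and record the departure from protocol 12.5.4 in SAP section 4.

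Align SAP 2.7.3 with 2.7.1 so that both data versions are named, keep LOCF as supportive, and show the numbers measured, discharged and dead by arm at each visit.

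The cost is SAP text and a small amount of extra analysis on data already collected. The model does not cure the late visits: those estimates still rest on the patients who remain in hospital, which is why the counts should be shown beside them.
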